9.5.3 Physical Examination

'Normal/NCS', 'CS' changes from baseline to end of cohort in physical examination results will be summarized in terms of frequency and percentage by cohort. The subjects with clinically significant results in physical examination will be listed.

9.5.4 Vital Signs

For vital signs results, the descriptive statistics for each cohort will be presented in collected visits. And the change of baseline and end of cohort will be presented.

9.5.5 Electrocardiogram

For each electrocardiogram results, the descriptive statistics for each cohort will be presented at each collected visit. And the change of baseline and end of cohort will be presented.

'Normal/NCS', 'CS' changes from baseline to end of cohort in electrocardiogram results will be summarized in terms of frequency and percentage by cohort.

9.5.6 FIX Inhibitor and Anti-drug Antibody Test

For FIX Inhibitor test and Anti-drug Antibody test, 'Positive', 'Negative' changes from 'Before injection' to 'After injection' in each results will be summarized in terms of frequency and percentage by cohort. If 'Positive' is confirmed once after injection, the subjects will be included 'Positive'.

In FIX Inhibitor test, if data is collected as 'LOQ', it will be analyzed as 'Negative', and if data is collected any numeric value, it will be analyzed as 'Positive'.

In Anti-drug Antibody test, data is collected as 'Positive', 'Negative'.

Additionally all FIX Inhibitor test and Anti-drug Antibody test results will be listed.

10. Derivation and Categorization for Variable

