5.1.10 FIX Inhibitor and Anti-drug Antibody Test

FIX inhibitor (or neutralizing antibody (NAb)) and anti-drug antibody test as well as a separate Bethesda assay shall be conducted in the central laboratories (inhibitor test, anti-drug antibody test: HTI, Bethesda assay: SCL) at the time of screening, 1st hospitalization, interim visit, 2nd hospitalization, and end of a cohort (with the exception of Bethesda assay at the time of screening). Tests for inhibitors and anti-drug antibodies to ISU304 and BeneFIX shall be conducted using a method developed by the sponsor.

Inhibitors to ISU304 and BeneFIX are detected through the Nijmegen method. When there is a positive result(>0.6 BU)⁽¹⁴⁾, a confirmatory test will be carried out. The inhibitor titer shall be recorded in Bethesda units (BUs). Anti-drug antibodies to ISU304 and BeneFIX are detected through a direct binding enzyme-linked immunosorbent assay (ELISA).

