7.2.3.6 FIX Inhibitors and Anti-drug Antibodies to the Investigational Products

The analysis of FIX inhibitors (neutralizing antibodies) and anti-drug antibodies shall be conducted for each subject by cohort at the designated central laboratory (HTI). A separate Bethesda assay shall be carried out at a different central laboratory (SCL). Changes in neutralizing antibodies and anti-drug antibodies before and after administration of the investigational products shall be summarized in terms of frequency, percentage, and titer.

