For following item, the number and proportion of subjects with following local AE and systemic AE according to reported term, other AE according to the SOC, PT and its 95% confidence interval and the number of following local AE and systemic AE according to reported term, other AE according to the SOC, PT will be estimated. If one subject has 2 or more AE in one category, it will be analyzed as one in the category. Also, the same subject may appear in different category in duplicate.

- Adverse Event
- Adverse Drug Reaction
- Serious Adverse Event
- Serious Adverse Drug Reaction
- Adverse Event of Special Interest

For AE, local/systemic/other AE, AESI, the number of AEs and its percentage (%) by each cohort

according to following AE item will be presented.

- Seriousness
- Severity
- Outcome
- Action Taken to IP
- Causal Relationship with IP
- Causal Relationship with others
- Treatment Given for AE

The following AEs will be listed.

- Local Adverse Drug Reaction
- Systemic Adverse Drug Reaction
- Other Adverse Drug Reaction
- Local Serious Adverse Event
- Systemic Serious Adverse Event
- Other Serious Adverse Event
- Adverse Event of Special Interest
- Adverse Event of subjects whose Early Withdrawal due to Adverse Event
- Other Adverse Event whose reported term is 'Nab positive' or 'ADA positive'
- Other Adverse Event whose PT term include 'injection site'
- Adverse Event (each patient)

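### SAP 9.5.6 replaces the protocol's inhibitor definition (>0.6 BU, then a confirmatory test) with any numeric value, omits the titer summary, and declares neither change

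*Combined protocol and SAP*

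**What the plan says.** **Protocol.** Section 5.1.10 detects inhibitors to ISU304 and BeneFIX by the Nijmegen method. Its rule begins "When there is a positive result(>0.6 BU" and continues that "a confirmatory test will be carried out". Titer is recorded in Bethesda units. Section 7.2.3.6 says that changes in neutralizing and anti-drug antibodies "shall be summarized in terms of frequency, percentage, and titer". It also provides for a second assay: "A separate Bethesda assay shall be carried out at a different central laboratory (SCL").

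**SAP.** Section 9.5.6 plans a before-to-after-injection shift table by cohort, with frequency and percentage. In the inhibitor test LOQ is Negative, "and if data is collected any numeric value, it will be analyzed as" Positive. At subject level, if Positive "is confirmed once after injection, the subjects will be included" as Positive. Anti-drug antibody (ADA) results are described as collected in two categories, positive and negative. On listings the section says: "Additionally all FIX Inhibitor test and Anti-drug Antibody test results will be listed". SAP 9.5.1 adds a listing of each "Other Adverse Event whose reported term is" NAb positive or ADA positive.

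SAP section 5, which records changes from the protocol's analyses, names one only: the PK/PD analysis is left to the central laboratory.

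**The concern.** Inhibitor formation is a key safety outcome here. Protocol 1.2.4 puts high-titer inhibitors among the most serious known risks of the comparator, 5.1.15 makes inhibitor generation an adverse event of special interest, and 6.1 lists a sponsor-confirmed inhibitor as a reason for withdrawal. The protocol therefore cares about three things: whether a result crosses a stated threshold, whether it is confirmed, and how high the titer is. The SAP's cohort table uses none of them. A reader of the study report would take its inhibitor rate to be the protocol-defined one, because the SAP says that it follows the protocol's method and section 5 signals no change on this outcome.

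**Working it through.** The plan states no figure to reproduce. The check compares the two rules and then sizes the difference.

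**1. Rules side by side**

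| Element | Protocol | SAP 9.5.6 |
|---|---|---|
| Positive inhibitor result | >0.6 BU (5.1.10) | any numeric value |
| Confirmatory test | follows a positive (5.1.10) | not mentioned |
| Summary | frequency, percentage, titer (7.2.3.6) | frequency, percentage |
| Assay | inhibitor test at HTI, separate Bethesda assay at SCL | 'FIX Inhibitor test', laboratory not named |
| Declared in SAP section 5 | – | no |

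**2. Where the cut-offs differ.** They disagree only on numeric values at or below 0.6 BU, a zone of width 0.6 − LOQ. The LOQ is not in the documents, so the values below are assumptions:

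- LOQ 0.2 BU: 0.6 − 0.2 = 0.4 BU
- LOQ 0.4 BU: 0.6 − 0.4 = 0.2 BU
- LOQ 0.6 BU: 0.6 − 0.6 = 0, leaving at most a value of exactly 0.6 BU

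With a higher LOQ, every reported number is above 0.6 BU and the two rules agree on it.

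**3. Effect in the shift table, assuming an LOQ of 0.2 BU (illustrative titers)**

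| Before | After | SAP coding | Coding at >0.6 BU |
|---|---|---|---|
| LOQ | 0.3 BU | Negative to Positive | Negative to Negative |
| 0.3 BU | 1.0 BU | Positive to Positive | Negative to Positive |
| LOQ | 1.0 BU | Negative to Positive | Negative to Positive, then confirmatory test |

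The first row is an over-count. The second is the reverse: a new inhibitor appears as no change. Such a subject can be in the trial, because exclusion 2 bars only a positive screening result, and 0.3 BU is not positive under 5.1.10.

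**4. Size per subject.** SAP 8.7 makes the cohort size the denominator, so one reclassified subject moves the rate by 1/n:

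- n = 3 (Cohorts 1 to 3; minimum of Cohort 5): 1/3 = 33.3 points
- n = 4 (possible in Cohort 5): 1/4 = 25.0 points
- n = 5 (Cohort 4; maximum of Cohort 5): 1/5 = 20.0 points

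One positive sample is enough under the ever-positive rule. Cohorts 1 to 3 have three planned samples after the first injection (interim visit, second hospitalization, end of cohort), and Cohorts 4 and 5 have one (end of cohort). The optional post-study visit can add one more in each.

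**5. Titer.** For the inhibitor test, BU values are recorded, so a summary is possible and is simply not planned. For ADA, the data that the SAP describes carry no titer, so 7.2.3.6 cannot be met from them.

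**The case against.** The strongest reply is that little may change in practice.

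- **The cut-off effect is conditional.** A reader might infer that the SAP will inflate the inhibitor count. The documents do not support that: the LOQ is unstated, and at 0.6 BU or higher the difference all but vanishes. This limits the claim but does not remove it, since the SAP gives no means of knowing which case applies.
- **Counting of unconfirmed positives is not shown.** A reader might also infer that the table will count them. The documents do not say whether the initial or the confirmed result is the one collected. The word 'confirmed' in the ever-positive rule could hint at confirmation. It more naturally means seen at least once, because no confirmatory test is named and any numeric value is then made Positive. The SAP is silent here rather than contrary.
- **No data are lost.** All results and the NAb-positive events are listed, and in cohorts of three to five a listing can be read by eye. This stands. But a listing is not the summary that 7.2.3.6 requires, and readers would have to rebuild the protocol-defined rate themselves.
- **Over-counting is the cautious direction for safety.** True after dosing, but a low value before dosing works the other way.
- **No trial decision is shown to turn on this table.** Withdrawal rests on sponsor confirmation, the committees review data after each cohort, and the SAP analysis follows database lock. To infer that withdrawals or dose escalation would be affected goes beyond the documents.
- **The mock tables are not available.** A titer column there cannot be excluded, though the SAP text plans none.

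**Conclusion.** The mismatch is real on the text, and the SAP should be corrected before the final analysis. Three parts need no assumption: the SAP's rule for a positive inhibitor result is not the protocol's, no titer summary is planned, and section 5 declares neither departure. The SAP text also gives the confirmatory result no role, whatever the LOQ.

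The effect on the reported rate is conditional. It needs an LOQ below 0.6 BU and at least one subject with a value between the two, or a collected result that is initial and later not confirmed. Each such subject shifts a cohort rate by 20 to 33 points. Masking of a new inhibitor further requires that low value before dosing and a true inhibitor afterwards in the same subject; the listing would still show the rise. The damage is confined to the cohort summary.

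**What to change.** In SAP 9.5.6:

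- Define Positive as >0.6 BU both before and after injection, as in protocol 5.1.10, and show numeric values at or below 0.6 BU as a separate category.
- State which assay the rule covers (HTI inhibitor test, SCL Bethesda assay, or both), with its LOQ.
- Report initial and confirmed positives separately where a confirmatory result is captured. Protocol 5.1.10 gives no criterion for confirmation, so the SAP should say what it takes as confirmed.
- Add a summary of titer in BU for the inhibitor test.

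In SAP section 5, declare any departure that remains, including that ADA is collected only as positive or negative, so no ADA titer can be summarised.

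The cost is a few lines of SAP text, one added summary and a slightly longer table for very small cohorts. No new sample or test is needed: the confirmatory test and BU recording are already in the protocol. The confirmed count does depend on that result reaching the database.

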10.1 Derivation

The calculation formulas are as follow. If statistical analysis requires additional calculation formula, SAP may not be revised but the calculation formula will be specified in TLFs.

Age

- In case the date of Informed Consent month/day < Date of Birth month/day:
Age = (Date of Informed Consent) - (Date of Birth) - 1
- In case the date of Informed Consent month/day \geq Date of Birth month/day:
Age = (Date of Informed Consent) - (Date of Birth)

Duration of Hemophilia B

- Year of 1st injection - Year of Diagnosis of Hemophilia B

Prior Medication

- Prior & Concomitant Medication Start Date < Date of 1st injection
- Prior & Concomitant Medication End date < Date of 1st injection
- Prior & Concomitant Medication Start Date is missing or unknown
- The following example will be included in Prior Medication.

Prior & Concomitant Medication Start Date	Prior & Concomitant Medication End date	Date of 1 st injection
2015-10-06	Ongoing	2015-10-15
2015-10-UK	2015-10-10	2015-10-15
2015-10-UK	Ongoing	2015-10-15
2015-10-UK	2015-10-UK	2015-10-15
UK	2015-10-20	2015-10-15
UK	UK	2015-10-15

Concomitant Medication

- (Prior & Concomitant Medication Start Date < Date of 1st injection) & (Prior & Concomitant Medication End Date \geq Date of 1st injection)

- (Prior & Concomitant Medication Start Date < Date of 1st injection) & (Prior & Concomitant Medication is 'Ongoing')
- Prior & Concomitant Medication Start Date \geq Date of 1st injection
- In case Prior & Concomitant Medication End Date is unknown, it is not defined Concomitant Medication.
- The following example will be included in Concomitant Medication.

Prior & Concomitant Medication Start Date	Prior & Concomitant Medication End date	Date of 1 st injection
2015-10-20	2015-10-30	2015-10-15
2015-10-06	Ongoing	2015-10-15
2015-11-UK	2015-11-UK	2015-10-15
2016-UK-UK	2016-UK-UK	2015-10-15
2015-10-UK	2015-10-20	2015-10-15
2015-10-UK	2015-11-UK	2015-10-15
2015-UK-UK	2016-UK-UK	2015-10-15

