9.4 Prior and Concomitant Medications

For following categorical variables, the descriptive statistics for each cohort will be presented.

- Prior Medication^a
- Concomitant Medication^b

^a Prior Medication: any drugs started from 3 months before screening visit to 1st injection

^b Concomitant Medication: any drugs started after 1st injection

The prior and concomitant medication will be classified as Level 1, Level 2 under the classification standard of recent version WHODDE. If one subject taken 2 or more medication in one category (Level 1, Level 2), it will be analyzed as one in the category. Also, the same subject may appear in different category in duplicate.

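### SAP 10.1 misclassifies some drugs certainly in use after the first injection, and conflicts with SAP 9.4 on what counts as concomitant

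*Combined protocol and SAP*

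**What the plan says.** SAP 9.4 defines a concomitant medication as "any drugs started after 1st injection", with no condition on the end date.

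SAP 10.1 gives the working rules. A record is Prior by any of three routes:
- the drug was begun earlier than the day of first dosing
- it was stopped earlier than that day
- "Prior & Concomitant Medication Start Date is missing or unknown"

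A record is Concomitant if it started before the first injection and ended on or after it, if it started before and is ongoing, or if it started on or after the first injection. The bullet that follows says, without qualification: "In case Prior & Concomitant Medication End Date is unknown, it is not defined Concomitant Medication".

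Two example tables come next, all with a first injection on 2015-10-15. The Prior table includes the row "UK 2015-10-20 2015-10-15" (start, end, first injection). UK is evidently the code for an unknown date or date part. SAP 8.6 states that missing and incomplete data are not replaced.

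**The concern.** A concomitant table should show what subjects were taking once dosing had begun. Where the dates prove use after dosing, the record belongs there, even if one date is missing. Section 10.1 fails this in two ways and disagrees with 9.4 in a third:

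1. A drug with an unknown start has no route into Concomitant, even when its end date shows that it was in use after dosing.
2. A drug with a known post-dose start and a wholly unknown end date appears to be excluded from both tables.
3. A drug started before dosing and continued through it is concomitant under 10.1 but not under 9.4.

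At stake is the accuracy of the medication tables, and whether two programmers would produce the same ones. SAP 9.4 plans no medication listing in which a dropped record would show up. Protocol 2.4.1 requires every concomitant medication to be recorded with its start and stop dates, so the tables would fall short of the data collected.

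**Working it through.** No sample size or error rate is involved. The check applies the rules of 10.1 to the SAP's own examples, then to the case that the examples leave out.

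**Inputs.** The rules and examples of SAP 10.1, with first injection 2015-10-15. The six Prior rows and seven Concomitant rows share one pair (2015-10-06 / Ongoing), so there are 6 + 7 − 1 = 12 distinct pairs.

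**Convention.** A date comparison counts only when it is certain, and a start that cannot be placed before or after dosing counts as unknown. The last column is the rule proposed under the fix: start certainly on or after dosing, or ongoing, or end certainly on or after dosing.

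| Start / end | SAP examples | Rules of 10.1 | Concomitant under the fix |
|---|---|---|---|
| 2015-10-06 / Ongoing | both | both | yes |
| 2015-10-20 / 2015-10-30 | Concomitant | Concomitant | yes |
| 2015-10-UK / 2015-10-10 | Prior | Prior | no |
| 2015-10-UK / 2015-10-20 | Concomitant | Prior | yes |
| 2015-10-UK / 2015-10-UK | Prior | Prior | no |
| 2015-10-UK / 2015-11-UK | Concomitant | Prior | yes |
| 2015-10-UK / Ongoing | Prior | Prior | yes |
| 2015-11-UK / 2015-11-UK | Concomitant | Concomitant | yes |
| 2015-UK-UK / 2016-UK-UK | Concomitant | Prior | yes |
| 2016-UK-UK / 2016-UK-UK | Concomitant | Concomitant | yes |
| UK / 2015-10-20 | Prior | Prior | yes |
| UK / UK | Prior | Prior | no |
| 2015-10-20 / UK | no example | neither | yes |

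**Reproducing the examples.** The rules match the SAP's placement in 9 of 12 pairs. The three misses are 2015-10-UK / 2015-10-20, 2015-10-UK / 2015-11-UK and 2015-UK-UK / 2016-UK-UK.

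**Unknown start, post-dose end.** UK / 2015-10-20 is Prior only, in the rules and in the examples. The end date is 20 − 15 = 5 days after dosing, so post-dose use is certain. The two classes are not meant to exclude each other, since 2015-10-06 / Ongoing is in both. The examples also conflict among themselves: 2015-10-UK / 2015-10-20 is Concomitant, but 2015-10-UK / Ongoing is listed only as Prior.

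**Post-dose start, wholly unknown end.** For 2015-10-20 / UK no Prior route applies: the start is known and not before dosing, and the end is not known to be before dosing. The start-date bullet would make it Concomitant, but the next bullet removes it. Starts of 2015-10-15 and 2015-11-UK give the same result. With the unknown-end bullet deleted, all three become Concomitant.

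**Dependence on programming.** If a SAS program compared raw dates, a missing date would sort lowest. Then 2015-10-20 / UK would be Prior only, because its missing end passes as earlier than dosing, and UK / 2015-10-20 would be in both tables.

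**Size.** With the cohort as denominator (SAP 8.7), one subject is 1/3 = 33.33 points at n=3 and 1/5 = 20.00 points at n=5.

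**The case against.** **The start-date bullet could prevail.** It carries no end-date condition, 9.4 agrees with it, and the unknown-end bullet might be meant only for drugs started before dosing, where the end date or ongoing status decides the class. No example shows a known post-dose start with a wholly unknown end. This stands in part: the loss from both tables follows from the bullet as worded, but the intention is not settled. What is certain is that the two bullets conflict.

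**Unknown starts could be resolved by logic.** UK / 2015-10-20 is concomitant whether the drug began before or after dosing, since each possibility meets a Concomitant bullet. That is true, and it is the only evident way that 2015-10-UK / 2015-10-20 reached the Concomitant examples. On that reading, however, UK / 2015-10-20 and 2015-10-UK / Ongoing should be there too. Neither convention reproduces all 12 pairs.

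**Stronger readings a reader might infer.** Four of these are not supported:
- That 2015-11-UK / 2015-11-UK contradicts the unknown-end bullet. It does not if unknown means wholly unknown, and the examples write partial dates differently from a bare UK.
- That oversight of prohibited drugs, or the reading of bleeding and thrombosis, depends on these tables. Protocol 2.4.2 and 6.1 handle prohibited drugs subject by subject. SAP 9.5.1 tabulates relationship to other causes and treatment given for each event, and neither uses the 10.1 dates. SAP section 7 considers no deviations beyond the analysis-set criteria, and the only set in the SAP is defined by dosing.
- That each misplaced record shifts a percentage by 20 to 33 points. Under 9.4 a subject counts once per category, so a second drug in the category removes the shift.
- That every drug with an unknown end should be concomitant. This would also move UK / UK and 2015-10-UK / 2015-10-UK, where post-dose use is not certain.

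The affected records should also be few: follow-up is 7 to 15 days, concomitant medications are checked at visits, and Ongoing is a separate code.

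**Conclusion.** The point holds as a defect in the SAP's derivation rules with limited consequences. The misplacement of UK / 2015-10-20 rests on the SAP's own example. That of 2015-10-UK / Ongoing rests on its absence from the Concomitant examples. The loss of a post-dose start with unknown end rests on reading the unknown-end bullet as written and on unknown meaning wholly unknown. The disagreement between 9.4 and 10.1 over drugs started before dosing and continued is plain on the text.

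The effect is confined to descriptive medication tables. The maximum of 33 points (n=3) or 20 points (n=5) assumes the planned cohort sizes, the cohort as denominator, and a misplaced record that is the subject's only one in its category. It does not carry over to tables by medication type, whose denominator under SAP 8.7 is the number of subjects with such medication and can itself change. The documents do not show how many records would be affected. The data stay in the CRF, and rescue drugs are recorded separately (protocol 5.1.14). The mock tables and listings in the SAP appendix are not in the text reviewed and might include a listing. No analysis set or safety endpoint changes.

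**What to change.** In SAP 10.1:
- Class a drug as concomitant if its start is certainly on or after the first injection (whatever the end date), or it is ongoing, or its end is certainly on or after the first injection.
- Limit the unknown-end bullet to drugs whose start is not certainly on or after the first injection.
- State that a drug may be both prior and concomitant, and whether unknown covers partial dates.
- Add UK / 2015-10-20 and 2015-10-UK / Ongoing to the Concomitant examples.

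In SAP 9.4, bring the definition into line, so that drugs started before dosing and continued are covered.

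This rule agrees with the SAP's existing Concomitant listing in 10 of the 12 example pairs. The two that change are the rows just named. UK / UK and 2015-10-UK / 2015-10-UK stay out.

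The cost is a few lines of SAP text and one derivation program, with no change to design or data collection. The downside is that a few records are counted in both tables.
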